**Diagnosing Obstructive Lung Disease with Point of Care Ultrasound-
A Cross-sectional, Diagnostic Accuracy Test**

Clinical Research Center, The Medical Intensive Care Unit, and Pulmonary Institute
Soroka University Medical Center,
Be'er-Sheva, Israel

Protocol SCRC23032

Version 1.2

September 2023

1 Investigator Signature Page

Study Title: Diagnosing Obstructive Lung Disease with Point of Care Ultrasound, A Cross-sectional, Diagnostic accuracy test

Protocol Version: Version 1.1

Protocol Date: 18 June 2023

Investigator's Responsibility

Prior to participation in the study, as the site principal investigator, I understand that I must obtain written approval from my local Ethics Committee (EC) and the hospital General Director.

As the site Principal Investigator, I must also:

1. Ensure that the study is not commenced until EC and hospital General Director approvals have been obtained.
2. Ensure that written informed consent is obtained from each patient prior to any data collection using the most recent EC-approved Patient Informed Consent Form.
3. Provide all required data and reports and agree to source document verification of study data with the patient's medical records.
4. Allow EC representatives, to inspect and copy any documents pertaining to this clinical investigation.

Investigator Signature

I have read and understand the contents of the study protocol and agree to abide by the requirements set forth in this document.

[name]

Investigator Name (print)

Soroka University Medical Center

Investigative Site (print)

[name]

Investigator Signature

June 18, 2023

Date

2 Protocol Summary

OBJECTIVE	To assess the accuracy of the Point of Care Ultrasound (POCUS) exam in diagnosing obstructive lung diseases (OLDs) compared to the gold standard pulmonary function test (PFTs)
STUDY DESIGN	A cross-sectional diagnostic accuracy test
INTERVENTION	None
SAMPLE SIZE CONSIDERATIONS	We aim to enroll a total of 200 patients. The calculation stems from the speculation that the Se of the test will be 85%, with a confidence interval of 90% and the maximal width of the interval will be up to $\pm 7\%$.
INCLUSION CRITERIA	
• Age 18 or above• Referral for full pulmonary function tests (PFTs)• Patients are willing and able to sign a written informed consent form.
EXCLUSION CRITERIA	
• Unable to give written informed consent.• Unable to remain supine.• Poor effort at PFTs• Subcutaneous emphysema
STUDY PROCEDURES	We plan to conduct random POCUS scans at the respiratory institute of Soroka University Medical Center on patients who are sent for pulmonary function tests (PFTs) for any reason and provide each patient with a sonographic score, comprised of several criteria (table 1).
DATA TO CAPTURE	Aside from the sonographic data, we plan to collect descriptive data from the hospital's medical records (i.e., smoking history, comorbidities, past radiographic exams, BMI, etc.) and the PFTs results.
OUTCOMES AND ANALYSES	The diagnostic accuracy of the POCUS examination, including sensitivity, specificity, positive predictive value (PPV), and negative predictive value (NPV) of obstructive lung diseases (OLDs) will be calculated using contingency tables with PFTs findings as the gold standard.
DATA MANAGEMENT AND ANALYSIS	The study will be overseen and managed by the Soroka Clinical Research Center.

Table of Contents

Page	Content
1	Title Page
2	Investigator signature page
3	Study protocol
5	Abbreviations and Definitions
6-7	Background
8-11	Design
12	Working hypothesis and objectives
12-13	Study population
13	Enrollment and patient screening
14	Study procedure and duration
15-16	Data to capture
17-19	Statistical Considerations and Analysis Plan
20-22	Adverse events
23-24	Ethical issues and subject confidentiality
25	References
26	Supplements

Abbreviations and Definitions

Abbreviation	Term
A4C	Apical 4-chamber (view)
COPD	Chronic obstructive lung disease
DLCO	Diffusing capacity for carbon monoxide
GS	Gold standard
LV	Left ventricle
mMRC	Modified Medical Research Council (Dyspnea Scale)
OLD	Obstructive lung diseases
PFTs	Pulmonary function test(s)
POCUS	Point of care ultrasound
PLAX	Parasternal long axis (view)
SX	Subxiphoid (view)

Definitions

3 Background

Point of care ultrasound (POCUS) is a valuable bedside tool for rapidly assessing multiple cardiorespiratory conditions (1). Its portability and ease of use make it particularly useful in acute care settings, where quick diagnostic information is crucial for optimal patient care (2). It has the advantage of immediate interpretation and clinical integration of the imaging results without radiation exposure. The POCUS assessment is considered quick and relatively simple even by non-radiologist novice trainees (3). It can closely monitor patients through repeatable exams in short periods, providing clinicians with an essential real-time image that can reinforce or weaken the initial diagnosis. Some even advocate its routine use as part of the physical exam and refer to it as the “new stethoscope” (4). The POCUS exam has been strongly validated as an accurate diagnostic tool in multiple lung pathologies such as pneumonia, pulmonary congestion, pleural effusions, and pneumothorax (5–8). It was found to be especially valuable in the acutely dyspneic patient, adding vital diagnostic information with great accuracy (9–11).

In contrast, POCUS has yet to be found as an efficient tool for diagnosing patients who suffer from obstructive lung disease (OLD) such as chronic obstructive pulmonary disease (COPD). This is probably due to air trapping in OLDs, considered the “great nemesis” of ultrasound. Nevertheless, based on multiple observations and personal clinical experience, we believe that POCUS can, in fact, efficiently recognize those patients with air trapping, mainly those with COPD.

In the last decade, we have used POCUS as part of the physical examination at the bedside regularly. We noticed that among COPD patients, we often detect very poor cardiac imaging on the parasternal long axis, apical four-chamber views (thoracal views), and relatively clear and noticeable cardiac imaging in the sub-costal view. In our experience, this group is characterized explicitly by multiple sonographic lung artifacts such as anterior predominant “A-lines” and the absence of “B-lines”. We hypothesize that the poor thoracal visibility is due to air trapping which interferes with the ultrasound waves. On the other hand, the clear cardiac images seen from the sub-costal view might be explained by the hyperinflated lungs shifting the heart downward, causing better cardiac imaging than is usually seen.

We plan to perform a cross-sectional observational study at the pulmonary institute of Soroka university medical center. We will conduct random POCUS scans on patients who are sent for pulmonary function tests (PFTs) for different suspected lung diseases.

A presumptive diagnosis will be made on-site based on the sonographic data collected. The accuracy of the POCUS in identifying OLD will be compared to the full PFTs, considered the

gold standard for diagnosing OLD and air trapping. We believe that the POCUS exam, identifying poor thoracal and exceptionally good subcostal views will accurately identify those with confirmed OLD and air trapping.

Our goal is to assess whether the POCUS exam accurately diagnoses OLD and air-trapping compared to standard PFTs. If so, this finding will have great applicability for identifying OLD patients early, even in remote areas where full PFTs are not accessible and referring them for further diagnostic workup.

4 Method

Design

In this cross-sectional study, we plan to conduct random POCUS scans at the respiratory institute of Soroka University Medical Center on patients who are sent for pulmonary function tests (PFTs) for any reason. The POCUS examiners will be blinded to the reason for referral or the patient's medical history in general. We plan to include all patients at the age of 18 or above who performed full PFTs and have signed the informed consent form. We intend to enroll 200 patients who meet the inclusion criteria and none of the exclusion criteria.

The examiners performing the scans will be skilled POCUS instructors with at least two years of experience in the field of cardiac and lung POCUS. The ultrasound examination will be conducted at a supine position and will include 2 parts:

1. An anterior chest scan to detect A-lines versus B-lines in lung zone 1 (Figure 1)
2. A 3-part cardiac scan consisting of a parasternal long-axis view, an apical 4-chambers view, and a sub-xiphoid view. (Figure 2).

[figure not shown]
Each patient will be met by the POCUS team once and scanned once, as described, in one lung zone and the three formal cardiac views.

Data from the medical records (i.e., smoking history, comorbidities, past radiographic exams, BMI, etc.) and the PFTs results will be collected by a third party, blinded to the POCUS exam. Eventually, the accuracy of the POCUS exam in identifying OLD will be compared to the gold standard of diagnosis, the full PFTs.

Figure 1 – The ultrasound probe is placed at zone 1 on the anterior chest.

Figure 2 – The formal 3-part cardiac exam (Parasternal long axis view (PLAX), Apical four-chambers view (A4C), and the subcostal view (sub-xiphoid, SX)

Diagnosis Considerations and Calculation

Chest scan grading

The anterior chest (Zone 1) will be examined bilaterally (see Figure 1) searching for A-lines (meaning aerated “open” alveoli) versus B-lines (which suggest alveolar flooding). A sonographic scan consistent with multiple A-Lines on both sides of the chest strengthens the diagnosis of OLD. Patients with three A-Lines or more will claim the maximal grade of 2 points on the corresponding side, meaning that a “perfect” score regarding the anterior chest is 4 (see Table 1).

Cardiac views grading

We will use three formal echocardiographic views for scoping the heart: The PLAX, A4C, and SX views (see Figure 2). Each view will provide the patient with an image quality score ranging from 0-2 depending on the quality of the view (see Table 1). The score for the different cardiac views, from “No discernable anatomy” to “Great view”, is relied on the level of detection of the left ventricular endocardial border. This criterion applies to all three cardiac views. We expect that a scan consisting of OLD will be characterized by poor PLAX and A4C views and great SX views. Therefore, maximal cardiac score (=6) will be granted to a scan consisting of a great (i.e. when the left ventricle (LV)endocardial border is clear) SX view and no discernable anatomy noticed in the PLAX and A4C views.

Grading synthesis

A sum of the cardiac and chest scans will give a final sonographic score between 0 to 10. A scan most consistent with OLD will be given a score of 10.

In the case of any abnormal finding in the chest or the cardiac POCUS, direct notification to the pulmonologist and the primary caregiver will be given by the research team, as well as written notification in the patient's electronic medical record. The patient and the primary caregiver will be notified that this exam is not a diagnostic cardiac exam focused only on detecting the level of the endocardial imaging quality. If b lines or abnormal left ventricular function are detected, the information will be transferred to involved teams.

Table 1

The Sonographic Score Components for the Diagnosis of OLD

	Right-sided Anterior chest (A-lines)	Left-sided Anterior chest (A-lines)	Parasternal long-axis view	Apical four- chamber view	Sub-xiphoid view
0	Multiple B-lines or No discernable A- lines	Multiple B- lines or No discernable A- lines	Great view (sub- endocardium noticed)	Great view (sub- endocardium noticed)	No discernable anatomy
1	1-2 A-lines	1-2 A-lines	Acceptable view	Acceptable view	Acceptable view
2	3 or more A- lines	3 or more A- lines	No discernable anatomy	No discernable anatomy	Great view (sub- endocardium noticed)

Obstructive lung disease (OLD definition)-

An umbrella term for diseases characterized by airway obstruction, airflow limitation, and in severe cases air trapping. Within this group and specifically among the adult population, the most common is chronic obstructive pulmonary disease (COPD)(12). Since most adult patients with air trapping encountered have COPD, we will use the terms COPD and OLD interchangeably.

4.1 Working Hypothesis

We hypothesize that a high sonographic score (8-10 points) will have at least an equal diagnostic accuracy compared to the reference diagnosis with PFTs.

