4.2 Objectives

4.2.1 Primary Objective

- To evaluate the validity (sensitivity and specificity) of the diagnostic accuracy of combined lung and cardiac ultrasound in obstructive lung disease (OLD), referring to PFTs as the diagnostic gold standard.

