4.6 Study Procedures

The study will be performed in a fully paired fashion, i.e., a direct comparison in which all study participants receive the index test (sonographic assessment) and the reference standard (PFTs).

This should enhance the resulting precision relative to the number of study participants. The three following steps are planned to take place at the same visit:

1. Enrollment, including obtaining written informed consent.
2. PFTs, performed as planned.
3. A sonographic evaluation comprised of both lung and cardiac POCUS scans, performed by an experienced sonographer, blinded to the patient's medical history or PFTs results.

Steps two and three can be replaced in order as long as the POCUS operator is blinded to the PFTs results. The PFT technician is not part of the study team and will be blinded to the POCUS findings as well.

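### Section 5.2 adopts no pre-stated score cut-off for a positive ultrasound, and section 4.1 hypothesizes at least equalling the test that defines truth

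*Combined protocol and SAP*

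**What the plan says.** The index test is a five-item score. Section 4 (Grading synthesis) states: "A sum of the cardiac and chest scans will give a final sonographic score between 0 to 10". No threshold for a positive test is given there or in Table 1.

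The one numeric cut-off in the protocol is in section 4.1. It calls 8 to 10 points a high score and hypothesizes that such a score "will have at least an equal diagnostic accuracy compared to the reference diagnosis with PFTs".

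PFTs are the only reference standard. Section 4.2.1 frames the primary objective as "referring to PFTs as the diagnostic gold standard". The Protocol Summary says the accuracy measures "will be calculated using contingency tables with PFTs findings as the gold standard". Section 4.6 has a fully paired design in which "all study participants receive the index test (sonographic assessment) and the reference standard (PFTs").

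The primary analysis in section 5.2 first calculates sensitivity, specificity, PPV and NPV for the sonographic score. It then builds an ROC curve with its AUC and evaluates performance at two points on the curve: 80% sensitivity and the knee-point. The four cells of the 2x2 table are defined by whether ultrasound and PFTs each detected OLD. OLD found by ultrasound alone is a false positive; OLD found by PFTs alone is a false negative. Section 5.2 gives no score that counts as a detection by ultrasound and does not mention 8 to 10.

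**The concern.** Sensitivity, specificity, PPV and NPV of a 0-10 score exist only once a cut-off is fixed. If the analyst follows 5.2 as written, the cut-offs actually named are the ones the data pick out. Accuracy measured in the patients who were used to choose the cut-off is on average too favourable. It also answers a different question from 4.1, which is about a score of 8 or more.

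The 4.1 sentence adds a problem of logic. It compares ultrasound with the test against which ultrasound is scored. Near-perfect ultrasound would still fall short of it, and the plan has no margin by which a small shortfall could be called acceptable. The stated hypothesis and the planned analysis do not meet.

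**Working it through.** **1. Where a positivity rule could come from**

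| Place | Rule for a positive ultrasound |
|---|---|
| Section 4, Grading synthesis and Table 1 | score 0-10, no threshold |
| Section 4.1 | 8 to 10 points |
| Section 5.1 | none (sensitivity of 85% assumed, cut-off not named) |
| Section 5.2, 2x2 definitions | none |
| Section 5.2, operating points | 80% sensitivity; knee-point (both read from the observed curve) |
| Section 5.3 | none |

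**2. What depends on the rule**

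For cut-off c, Se(c) = P(score ≥ c given OLD) and Sp(c) = P(score < c given no OLD). PPV and NPV follow from these and the share with OLD. The AUC uses all cut-offs, so it does not depend on the choice.

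A 0-10 score has 11 levels and 10 non-trivial cut-offs, so exactly 80% sensitivity may not be attainable. Where it is, sensitivity has been set by choice and only the specificity there is informative.

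**3. How much the choice can matter (illustration)**

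The documents give no score distribution. Two are assumed here: normal scores rounded to 0-10, with (A) means 7 and 4.5, SD 2, and (B) means 8 and 5, SD 1.8, for patients with and without OLD.

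| Cut-off | A: Se / Sp | B: Se / Sp |
|---|---|---|
| ≥ 8 | 40.1% / 93.3% | 60.9% / 91.8% |
| ≥ 7 | 59.9% / 84.1% | 79.8% / 79.8% |
| ≥ 6 | 77.3% / 69.1% | 91.8% / 60.9% |
| ≥ 5 | 89.4% / 50.0% | 97.4% / 39.1% |

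In A no cut-off gives 80% sensitivity: the neighbours are 77.3% and 89.4%.

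For each case, 20,000 studies of 200 patients were simulated, with 70 or 100 OLD patients (assumed). The knee-point was taken as the maximum of Se + Sp − 1, which is an interpretation of 5.2.

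| Case | Observed Se + Sp − 1 at knee | True value at that cut-off | Difference | Knee falls on ≥ 8 |
|---|---|---|---|---|
| A, 70 OLD | 0.4781 | 0.4519 | 0.0262 | 0.5% |
| A, 100 OLD | 0.4767 | 0.4525 | 0.0242 | 0.3% |
| B, 70 OLD | 0.5996 | 0.5827 | 0.0169 | 9.3% |
| B, 100 OLD | 0.5992 | 0.5840 | 0.0152 | 7.0% |

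The optimism is modest. The larger effect is that the reported point is seldom the one in the hypothesis.

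**4. The comparison in 4.1**

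With PFTs as truth, PFT sensitivity and specificity are 100% by construction. The difference, ultrasound minus PFT, is at most 0 for each. It is 0 for both only if no patient is discordant.

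To see what a perfect result would show, OLD counts are needed. Section 5.1 (85%, 90% interval, ±7%) gives z²p(1−p)/h² = 1.645² × 0.85 × 0.15 / 0.07² = 70.4, so 71 OLD patients. The stated total of 200 follows if 71/200 = 35.5% have OLD, a share the plan does not state. At 95% confidence the same formula gives 1.96² × 0.1275 / 0.0049 = 99.96, so 100 OLD patients, or 200 in total at 50%. Nothing here turns on which was meant.

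With no false negatives, the exact two-sided 95% lower limit for sensitivity is 0.025^(1/n): 94.9% for n = 71 and 96.4% for n = 100. Even a perfect sample leaves a gap to 100% that needs a margin to judge, and none is given.

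**The case against.** The strongest reply is that the plan is an estimation study. The primary objective, the precision-based sample size and the listed measures are all estimates against PFTs, and no analysis tests 4.1. This stands: those measures are sound, and rewording 4.1 changes no estimate. Taken alone, the wording is minor.

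A second reply is that 8 to 10 can be inferred for the first step of 5.2, since the four measures come before the ROC curve, and that the two operating points are themselves pre-specified methods. Both are fair. But an inferred rule is not a stated one, and 5.2 does not say how the two points relate to 8 to 10 or which result is primary.

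Four stronger readings are tempting and not supported:

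- *No result could support 4.1.* A perfect tie would satisfy it.
- *The plan contains rival decision rules.* The Background says "A presumptive diagnosis will be made on-site based on the sonographic data collected" and expresses the belief that the examination, "identifying poor thoracal and exceptionally good subcostal views will accurately identify those with confirmed OLD" and air trapping. These are narrative. Section 5.2 names the sonographic score as the test evaluated, and the view pattern is built into that score.
- *The 85% in 5.1 contradicts 4.1.* That holds only if 85% refers to a score of 8 or more, which 5.1 does not say.
- *The sample size is wrong.* The calculation omits the share with OLD, but plausible values give 200.

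**Conclusion.** The point holds and should be fixed before analysis. The main fault is in 5.2: it adopts no score cut-off for the 2x2 table, and the only operating points it names are data-derived. As written, the headline sensitivity, specificity, PPV and NPV may be somewhat optimistic and need not address the hypothesis. The AUC is not affected.

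The size cannot be taken from the documents. Under the assumed distributions, optimism was about 0.015 to 0.026 in Se + Sp − 1, and the knee-point matched the 4.1 cut-off in 0.3% to 9.3% of simulated studies. Other distributions would give other figures.

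The lesser fault is in 4.1: accuracy equal to PFTs could be observed only with zero discordant patients, and no margin exists for anything short of that. This part is a matter of logic and rests on no assumption.

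**What to change.** **Section 5.2.** Subject to the sponsor confirming that 8 or more is the intended rule, add: *A sonographic score of 8 or more defines a positive POCUS for the 2x2 table. Sensitivity, specificity, PPV and NPV at this cut-off, with exact 95% confidence intervals, are the main result and the analysis of the working hypothesis. Results at 80% sensitivity (or the nearest attainable value) and at the knee-point are data-derived and exploratory.*

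**Section 4.1.** Replace the comparison with PFT accuracy by: *A sonographic score of 8 or more identifies PFT-defined OLD, with sensitivity and specificity estimated against PFTs.* This relies on a written PFT criterion. The OLD definition in section 4 is only a description ("An umbrella term for diseases characterized by airway obstruction, airflow limitation, and in severe cases air trapping"), so the criterion should be added.

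**Sponsor check.** Say whether the 85% in 5.1 refers to a score of 8 or more.

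**Optional.** The new 4.1 sentence has no pass mark. If the sponsor wants a testable hypothesis, minimum sensitivity and specificity must be fixed before analysis. The documents give no values, and the sample size, planned for precision only, would need its own check. For orientation, an observed sensitivity of 85% has an exact 95% interval of 73.4% to 92.9% with 60 OLD patients (51/60), 76.5% to 91.4% with 100 (85/100) and 77.3% to 90.9% with 120 (102/120); these counts are assumed.

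**Cost.** A few sentences, with no change to patients or measurements, and none to the sample size unless minimum values are set. The claim becomes more modest, and the figures at 8 or more may be less favourable than at the data-chosen points.

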4.2 Objectives

4.2.1 Primary Objective

- To evaluate the validity (sensitivity and specificity) of the diagnostic accuracy of combined lung and cardiac ultrasound in obstructive lung disease (OLD), referring to PFTs as the diagnostic gold standard.

4.2.2 Secondary Objective

- To estimate the association between the sonographic score and the most recent (<5 years) computed tomography (CT) scan score (i.e., emphysema score).
- To estimate the association between the sonographic score and the patient's subjective severity of dyspnea (estimated by the mMRC scale).
- To estimate the association between the sonographic score and the patient's diffusion lung capacity (DLCO).
- To determine the sonographic components that are the most sensitive for the diagnosis of COPD.
- To assess the additive value of the patient's smoking status to the diagnostic accuracy of the sonographic score.

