4.8 Data to Capture

4.8.1 Required Data

We aim to collect the sonographic data as well as the PFT results for each participant. Furthermore, we plan to gather descriptive data from the medical records including –

1. Age -continuous variable. Values: above 18.
2. Gender - dichotomic variable (Female=1, Male=0).
3. BMI - continuous variable.
4. Smoking history (pack years)- continuous variable.
5. Comorbidities - nominal variable. Values: dichotomic variable (Yes=1, No=0)
6. Hypertension – ordinal variable. (0=Normal, 1=Elevated, 2= Stage 1, 3 = Stage 2, 4= Hypersensitive crisis). Values: 0=systolic<120 & diastolic<80, 1=systolic=120-129 & diastolic<80, 2=systolic=130-139 & diastolic 80-89, 3=systolic>140 & diastolic>90, 4= systolic>180 & diastolic>110.
7. Diabetes - dichotomic variable (Yes=1, No=0)
8. Other Lung diseases (such as cystic fibrosis, bronchiectasis, Interstitial lung disease, etc) - dichotomic variable (Yes=1, NO=0)
9. Ischemic Heart Disease - dichotomic variable (Yes=1, No=0)
10. Degree of dyspnea (based on the mMRC Dyspnea Scale) - ordinal variable (1=Grade 1 ,2= Grade 2, 3=Grade 3, 4 =Grade 4). See supplements for mMRC dyspnea scaling system.
11. Hemoglobin level (g%) - continuous variable.
12. Latest Venous/Arterial pH- continuous variable.
13. Latest Venous/Arterial HCO3- - continuous variable.
14. Latest Venous/Arterial pCO2- continuous variable.
15. Latest Arterial pO2 - continuous variable.
 - a. The blood attributes under investigation will be derived retrospectively from the electronic medical record of the current hospitalization, and blood tests will not be performed as part of this trial.
16. Past computed tomographic scans (most recent and up to 5 years prior) - ordinal variable (0= no emphysema (score 0),1= \leq 25% emphysema (score 1),2= \leq 50% emphysema (score 2), 3= \leq 75% emphysema (score 3),4= $>$ 75% emphysema (score 4)).

All required data for this study will be collected via electronic case report forms (eCRF).

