5.1 Sample Size Considerations

In this study, the sample size calculation was aimed to ensure an accurate estimate of sensitivity (Se) and specificity (Sp) of the POCUS examination vs the gold standard PFTs. We aim to enroll a total of 200 patients. The calculation stems from the speculation that the Se of the test will be 85%, with a confidence interval of 90% and the maximal width of the interval will be up to $\pm 7\%$.

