- To determine the sonographic components that are the most sensitive for the diagnosis of OLD - we can use a logistic regression analysis. The regression will provide estimates of the effect of each sonographic component on the probability of being diagnosed with OLD. In this analysis, we can use the sonographic components as predictor variables and OLD diagnosis as the outcome variable.
- To assess the additive value of the patient's smoking status to the sonographic score's diagnostic accuracy- will be based on a logistic regression analysis. In this analysis, we can use the sonographic score and smoking status as predictor variables and OLD diagnosis as

the outcome variable. The regression will provide estimates of the effect of each predictor on the probability of being diagnosed with OLD, as well as an estimate of the additional effect of smoking status beyond the sonographic score.

All statistical tests and/or confidence intervals, as appropriate, will be performed at $\alpha=0.05$ (2-sided) or $\alpha=0.025$ (1-sided), except for those specified otherwise. All p-values reported will be rounded to three decimal places. All statistical analyses will be conducted using SPSS 29.0 statistical software (IBM Corp Armonk, NY, USA).

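### Accuracy against PFTs alone does not show what the scan adds to age, smoking and dyspnea, which is what the claim for settings without PFTs needs

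*Combined protocol and SAP*

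**What the plan says.** - **Intended use.** The Background (section 3) states the goal as accuracy against PFTs and continues, conditionally on success, that "this finding will have great applicability for identifying OLD patients early, even in remote areas where full PFTs are not accessible", with referral for further workup.
- **Primary analysis.** Sections 4.2.1 and 5.2 compare the score with PFTs only: sensitivity, specificity, PPV, NPV, and the ROC curve with its AUC.
- **Added value.** The last objective in 4.2.2 is "To assess the additive value of the patient's smoking status to the diagnostic accuracy of the sonographic score". Section 5.2 implements it as a logistic regression of OLD on score and smoking status. It promises an effect estimate for each predictor and "an estimate of the additional effect of smoking status beyond the sonographic score".
- **Clinical data.** Section 4.8.1 lists age, gender, BMI, mMRC grade and "Smoking history (pack years)- continuous variable". Apart from smoking, none of these enters a model for OLD. Section 5.2 uses mMRC only for its association with the score.

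**The concern.** Where PFTs are out of reach, the alternative to POCUS is not ignorance but a short history. A score can separate OLD from non-OLD well and still mostly repeat what age, pack-years and breathlessness already show. The plan could then report a respectable AUC, and readers could take the Background statement as confirmed, although the scan's contribution to the referral decision had not been measured.

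The added-value objective comes closest to this question but takes the score as the base and smoking as the addition. It also speaks of diagnostic accuracy, while its analysis yields regression effects. An adjusted odds ratio does not say how much discrimination improves. Finally, the predictor is called smoking status, whereas the captured variable is pack-years.

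**Working it through.** **1. What each analysis can answer.**
- Score against PFTs: how accurate is the scan alone? Answered by the primary analysis.
- Score and smoking in one model: is the score associated with OLD after adjustment for smoking, and the reverse? Both come from the same fit.
- Age, smoking and dyspnea without the scan: how accurate? Not planned.
- Those three with and without the scan: how much accuracy is gained? Not planned.

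**2. The plan's own figure.** The documents give no AUC or added-value target. The only relevant number is the sample size (section 5.1: "We aim to enroll a total of 200 patients"), which bears on feasibility. With sensitivity 0.85, 90% confidence and ±7 points read as a half-width, n = z²p(1−p)/d² = 1.645² × 0.85 × 0.15 / 0.07² = 70.4, so 71 patients with OLD. A total of 200 then needs a prevalence of 71/200 = 35.5%, which is not stated. This does not decide the present point.

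**3. How far stand-alone accuracy and added accuracy can differ.** All AUCs and correlations here are assumptions. In a binormal model, d = √2·Φ⁻¹(AUC) for each marker. With within-group correlation ρ, D² = (d₁² + d₂² − 2ρd₁d₂)/(1 − ρ²), and the combined AUC is Φ(D/√2). AUCs of 0.75 and 0.80 give d = 0.9539 and 1.1902.
- ρ = 0: D² = 0.9099 + 1.4166 = 2.3265; combined AUC = 0.860.
- ρ = 0.6: D² = (2.3265 − 1.2 × 0.9539 × 1.1902)/0.64 = 0.9641/0.64 = 1.506; combined AUC = 0.807.

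| Assumed clinical AUC | Assumed score AUC | ρ | Combined AUC | Scan adds |
|---|---|---|---|---|
| 0.75 | 0.80 | 0 | 0.860 | 0.860 − 0.75 = 0.110 |
| 0.75 | 0.80 | 0.6 | 0.807 | 0.807 − 0.75 = 0.057 |
| 0.80 | 0.75 | 0.6 | 0.807 | 0.807 − 0.80 = 0.007 |

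In the last row the plan would report a score AUC of 0.75, and no planned accuracy measure would show that the scan adds almost nothing.

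**4. Whether 200 patients can carry the comparison.** Age, pack-years, mMRC (as a linear term) and score make four parameters. For an assumed OLD prevalence of 30% to 60%, the smaller outcome class has 60 patients (at 30%) to 100 (at 50%), which is 60/4 = 15 to 100/4 = 25 per parameter. Simulated power of a likelihood-ratio test for the score (N = 200, two-sided 0.05, prevalence 35.5% or 50%, 400 replicates per scenario) was about 85% or more across score AUCs of 0.75 to 0.80, clinical AUCs of 0.70 to 0.80 and correlations of 0 to 0.6. The one exception was the last row of the table, at 41% to 47%. The simulation treats the clinical information as one continuous predictor, so these powers are somewhat optimistic.

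**The case against.** **The score is already set against clinical information.** This stands in part. A joint logistic model has no direction: the fit that gives smoking beyond the score also gives the score beyond smoking. A reader might infer that the plan never relates the scan to history, and section 5.2 does not support that. What is missing is narrower: age and dyspnea, and any measure of accuracy gained.

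**The applicability sentence is only motivation.** It is conditional, speaks of referral for further workup, and is not an objective, hypothesis or endpoint. Stand-alone accuracy is a legitimate first question for a cross-sectional accuracy study. All of this stands. A reader might infer that the design cannot support the intended use at all, or that the primary objective is wrong. Neither follows, because accuracy against PFTs is necessary evidence. But the sentence draws the use from accuracy alone, and that step is not sufficient.

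**The illustration proves nothing about this trial.** Correct: it shows only that the two quantities can diverge. Two over-readings should be avoided. The gap between what the scan adds to history and what history adds to the scan is, for any assumed pair, just the difference between the two assumed AUCs, so it is not a result. And the clinical AUC stands for all the clinical information, so the table says nothing about smoking alone.

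**A clinical comparator here would not settle remote use.** This stands. Everyone enrolled was referred for full PFTs at a hospital institute (4.3, 4.3.1), so a gain found here need not carry over to unreferred patients.

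**The smoking label is minor.** Agreed. It needs one definition, no more.

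**Conclusion.** The point holds as a limited one. The primary analysis is sound in aim, but stand-alone accuracy together with a score-and-smoking regression is not sufficient for the Background statement on settings without PFTs, because the accuracy the scan adds to age, smoking and dyspnea is not estimated. The size in this trial is unknown. Under the assumptions shown, the gain could be as large as 0.110 or as small as 0.007 in AUC, and the planned accuracy measures would not tell these cases apart. The absence of a clinical-only comparison rests on the text alone; only the illustration of size rests on assumed AUCs, correlations and the binormal model. The change is worth making before analysis but does not affect the validity of the primary endpoint.

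**What to change.** Revise the last objective in 4.2.2 and its analysis in 5.2:

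1. Prespecify a clinical base model for PFT-defined OLD with age, pack-years and mMRC grade, then add the sonographic score. Fit both models to the same patients.
2. Report each model's AUC, a likelihood-ratio test for the score, and the AUC difference with a bootstrap, optimism-corrected 95% CI. The models are nested and are fitted and evaluated in the same data, so an uncorrected comparison of the two AUCs is not enough.
3. Keep smoking added to the score as the reverse contrast, also as an AUC change, with pack-years as the smoking variable.
4. Code mMRC 0 to 4 as in the Supplements (section 10); 4.8.1 lists only 1 to 4, so grade 0 has no code.
5. Use the same PFT definition of OLD as the primary analysis, and state it: the definition below Table 1 gives no PFT criterion.
6. In the Background, condition the applicability statement on this gain, and say that transfer to remote, unreferred patients remains untested.

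Cost: revised wording, a little more analysis, and no new variables. The mMRC recoding must reach the eCRF, and the sponsor should confirm that the software named in 5.2 can run the bootstrap. The gain may look less favourable than the stand-alone AUC. If the comparison is not wanted, the minimum is to narrow the Background statement to accuracy among patients referred for PFTs.
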